9.17 Subject Exit, Withdrawal or Discontinuation

Should a subject withdraw or be lost to follow-up, the designated study personnel will complete the Study Exit CRF, including:

- Date of Study Exit
- Subject status (i.e., reason for withdrawal)

At any time between enrollment and study completion, study personnel may complete the Study Exit CRF. The number (minimum 2) and type of attempts to contact subject (email, text, call, etc.) prior to Lost to Follow-up designation should be documented in the subject's medical record.

9.17.1 Study Exit

A study exit eCRF is required for all subjects. Prior to exiting a subject from the study, it is recommended to follow the subject until all ongoing system and/or procedure related AEs are resolved or unresolved with no further actions planned. Following exit, subjects will continue to receive standard medical care. Upon exiting from the study, no further study data will be collected or study visits will occur for the subject. All data available through the time of the subject's exit will be used for analysis.

Subjects are urged to remain in the study as long as possible but may be exited from the study for any of the following situations:

- Study completed
- Subject lost to follow-up

Medtronic Business Restricted

- Subject death
- Subject did not meet inclusion/exclusion criteria
- Investigator chose not to use the Novapak Nasal Sinus Packing and Stent device
- Subject did not provide consent (or data use protection authorization where required)
- Subject chooses to withdraw (e.g., consent withdrawal, relocation to another geographic location)
- Investigator deems withdrawal necessary (e.g., medically justified, inclusion/exclusion criteria not met, failure of subject to maintain adequate study compliance)

The following information is required to be collected at study exit:

- Date of Study Exit
- Reason for exit (subject status)
 - AE related
 - Covid related

If discontinuation is because of safety or lack of effectiveness, the subject shall be asked to be followed for collecting safety data outside the clinical investigation.

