9.4 Subject Screening

All subjects that are considered for the study should be screened based on the inclusion/exclusion criteria. The reason for non-eligibility, as determined by the Investigator should also be recorded on appropriate eligibility eCRF. The screening information serves as a method for Medtronic to assess selection bias in the trial and other reasons for subject rejection (e.g., subject with a known shellfish allergy). Additional shellfish allergy criteria questions have been added to determine the potential subjects' eligibility based on their previous exposure risk to shellfish and other organisms containing the tropomyosin protein. If the potential subject is completely naïve to shellfish allergic status the site primary investigator will assess the risk based on responses to screening questions and may either include, exclude or test the subject for shellfish allergy potential.

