9.13 Assessment of Efficacy

The following parameters will be used to assess the effectiveness of the Novapak device used according to device indications:

Adhesions – in order to show that Novapak acts a nasal stent to separate tissue or structures compromised by surgical trauma and separate and prevent adhesions between mucosal surfaces in the nasal cavity the study physician will count the number of adhesions present and grade the sinuses using the ordinal scale method published by Valentine 2010.

Control of bleeding – in order to show that Novapak controls minimal bleeding the study physician will grade the bleeding post-surgery and prior to packing using the Boezaart Surgical Field Grading Scale. After inserting the Novapak product with irrigation to hydrate the product the bleeding will be graded again using the same scale.

During the day 14 visit the physician will be asked if any bleeding is observed during the exam and prior to any debridement procedure.

Progression of healing – The Lund Kennedy endoscopic grading system will be used to show that Novapak acts as an adjunct to aid in the natural healing process. The physician will perform an endoscopic exam prior to surgery (to establish a baseline), at day 14 and day 30 visits (to show progressive healing).

Residual Novapak – Novapak dissolves naturally with daily irrigation. Any residual Novapak in the nasal cavity will be recorded at the 14 day visit and compared to the subject compliance to the daily irrigation log.

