9.17.5 Investigator Withdraws Subject

No subjects should be withdrawn by investigators unless compelling medical justification is present. It is recommended investigators discuss any withdrawals with the study team prior to withdrawing subjects.

Medtronic Business Restricted

Early removal of Novapak (within the first 7 days of application) alone may not be a reason for subject withdrawal. If an Investigator Withdrawal is necessary, the following data should be collected prior to subject withdrawal if possible:

- Date of study exit
- Reason for subject withdrawal

10. Risks and Benefits

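### CIP 9.17.1 allows study exit after packing for unmet criteria or poor compliance and ends follow-up there, which conflicts with 9.17.5 and may lose outcome-related data

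*Protocol*

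**What the plan says.** CIP 9.17.1 (Study Exit) gives two routes that matter here. One stands alone: "Subject did not meet inclusion/exclusion criteria". The other is investigator withdrawal: "Investigator deems withdrawal necessary (e.g., medically justified, inclusion/exclusion criteria not met, failure of subject to maintain adequate study compliance". Neither separates the period before device placement from the period after it. CIP 9.17 lets the exit form be completed at any point between enrolment and study completion.

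The same section sets the consequence: "Upon exiting from the study, no further study data will be collected or study visits will occur for the subject". It also says what is retained: "All data available through the time of the subject's exit will be used for analysis". It recommends, but does not require, following ongoing system- or procedure-related AEs before exit. Subjects who discontinue for safety or lack of effectiveness are to be asked to accept safety follow-up, but outside the investigation.

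CIP 9.17.5 (Investigator Withdraws Subject) takes a stricter line: "No subjects should be withdrawn by investigators unless compelling medical justification is present". It adds that early removal of the packing may not by itself justify withdrawal, and it recommends discussing withdrawals with the study team first.

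**The concern.** The two sections give different rules for the same decision. In 9.17.1, medical justification is one example among three, so the other two are offered as grounds in their own right. Poor compliance is not a medical reason. An unmet criterion sometimes could be one, but need not be.

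The difference matters because, on the CIP's own account, both grounds are related to outcome. CIP 9.12 says daily irrigation is needed for the packing to dissolve fully. CIP 10.2 says shellfish screening is there to reduce hypersensitivity to the chitosan component. CIP 9.4 adds discretion: for a subject whose shellfish status is unknown, the investigator "may either include, exclude or test the subject for shellfish allergy potential". It is therefore foreseeable that an allergy will be discovered after packing. Subjects who leave on these grounds may not resemble those who stay, and what happens to them after exit is not observed.

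**Working it through.** The plan states no figure on this point, and CIP 13.5 says the minimum of 75 subjects was not derived statistically, so there is nothing to reproduce. The check is mainly textual.

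**1. What stops at exit.** CIP 9.17.1 ends visits and data. CIP 11.1 ends AE collection at the 30-day visit or exit, whichever is earlier. CIP 11.3 ends follow-up of open AEs at exit. CIP 4.1.1.1.1 treats the withdrawal date as study completion for the primary safety endpoint. These are consistent: no AE arising after exit enters the study data.

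**2. What is lost, by time of exit.**

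| Exit after placement | Kept | Lost |
|---|---|---|
| Before the Day 14 visit | Day 0 data; AEs to exit | Day 14 and Day 30 assessments; later AEs |
| At the Day 14 visit | Also Day 14 Lund-Kennedy, SNOT-22, adhesions, bleeding and residual product | Day 30 Lund-Kennedy, SNOT-22 and adhesions; later AEs |

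**3. When non-compliance becomes known.** Under CIP 9.9 and 9.12 the irrigation log is handed in and inspected at Day 14. Under CIP 9.13 residual product "will be recorded at the 14 day visit and compared to the subject compliance to the daily irrigation log". These happen at the same visit, and none is scheduled between Day 0 and Day 14. An exit based on the log therefore usually falls in the second row. The first row needs earlier knowledge, for example from an unscheduled visit (CIP 9.10). An exit for unmet criteria has no such anchor and can come at any time.

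**4. Table 8 windows.** CIP 11.1 exempts listed post-surgical events from reporting unless they worsen or persist beyond a window, for example 7 days for inflammation and swelling and 10 days for nasal congestion. The longest window is 10 days; the Day 14 visit opens at 14 - 2 = 12 days. A subject who exits inside a window with such an event ongoing contributes nothing, even if the event later persists past the window. This loss also requires exit before the first scheduled visit.

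**5. How the analysis treats the gap.** CIP 13.1 and SAP 7.4 use no imputation and drop a subject from any analysis for which data are missing. SAP 7.9.1 evaluates safety by numbers of AEs. A post-exit AE can only be missing from such a count, so the count can only be equal or too low. For the Day 30 scores the direction of any bias cannot be read from the documents.

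**6. Leverage of one subject (not an estimate).** With 75 treated subjects, one subject's unobserved event changes a proportion by 1/75 = 1.3 percentage points. Suppose three subjects each had their only primary-endpoint AE after exit. The full-follow-up result would be 3/75 = 4.0% (exact 95% interval 0.8% to 11.2%). The reported result would be 0/75 (upper limit 4.8%) if they stay in the denominator, or 0/72 (upper limit 5.0%) if they are dropped. Three subjects and the 95% level are assumptions; the documents give neither.

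**The case against.** The strongest reply is that the practical loss is small and partly guarded against.

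- **Subjects removed altogether.** A reader might infer that exited subjects vanish from the results. Under the CIP they do not, because data to exit are used. If a subject reacts to the device, is then found to be allergic and is exited, the reaction itself is retained. Such an exit might also count as a safety discontinuation, with follow-up requested. SAP 7.1.3, which restricts the analysis set to subjects meeting the criteria, could exclude that subject, but that is a separate issue. Correcting it would not recover visits that never took place.
- **Residual-product result biased.** A reader might infer that poor irrigators disappear before the Day 14 check and flatter the device. The schedule does not support this as the usual course (step 3). The CIP also compares residual product with compliance; losing some non-compliant subjects thins that group but does not by itself bias rates within it.
- **Pre-treatment reading.** Eligibility is confirmed after consent (CIP 9.7), and the stand-alone eligibility bullet sits beside the one for not using the device. It may be meant for exits before treatment. That is plausible, but the text does not say so.
- **Other safeguards.** Subjects are urged to stay, late visits are preferred to missed ones (CIP 9.3), unmet criteria are already a reportable deviation (CIP 9.16), and each analysis reports its number of subjects.

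These points limit the consequence. They do not remove the conflict between 9.17.1 and 9.17.5. Nor do they supply study data after exit: the pre-exit AE follow-up is only recommended and concerns ongoing events, and the safety follow-up lies outside the investigation and does not cover exits made for eligibility or compliance.

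**Conclusion.** The conflict is in the text and should be resolved. Followed as written, 9.17.1 allows a packed subject to be exited for a reason that the CIP links to outcome, and later AEs and usually the Day 30 assessments then go uncollected. Day 14 residual-product data are at risk only if non-compliance is known before that visit.

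The missing follow-up may be informative. That is an inference from the CIP's statements on irrigation and shellfish allergy; the documents give no event rates by compliance or allergy status and no expected number of such exits. The size therefore cannot be estimated, and the figures in step 6 show only how much a few subjects weigh in a study of 75. The documents do not support saying that the highest-risk subjects are removed from the data, or that every result leans in the device's favour.

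**What to change.** Edit CIP 9.17.1 to agree with 9.17.5:

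1. Make unmet eligibility criteria a ground for study exit only before Novapak is placed, both in the stand-alone bullet and in the investigator-withdrawal examples.
2. Delete inadequate compliance as a reason for investigator withdrawal from the study.
3. State that, after placement, a subject found ineligible or non-compliant stays in the scheduled Day 14 and Day 30 visits and AE collection unless the subject withdraws consent or 9.17.5 applies, and that a deviation is recorded.

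The bullet on the investigator choosing not to use the device needs no time limit, since it already means that nothing was placed. Death and loss to follow-up are unaffected. The change concerns study follow-up only, not treatment.

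The cost is a few sentences in one section and, for a small number of subjects, completing at most two visits that are already scheduled.

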4.1.1.1.1 Primary Device Safety Endpoints

The primary safety endpoint is an assessment of all AEs that are directly attributable to the device and/or for which cause cannot be determined, and that meet the definition of designated primary safety endpoint AEs (see section 11.4) that will be used to determine the point estimate and its confidence interval. This endpoint will be analyzed by calculating the point estimate with a confidence interval of its rate. All AEs will be collected for each subject from time of treatment until their study completion.

Study completion for each subject is the time point at which the 30-day follow-up visit is completed, outstanding AE follow-up (if any) has been concluded, and a Study Exit CRF has been completed. For subjects who withdrew or were lost to follow-up, study completion will be the date of withdrawal or the date the subject meets the definition of lost to follow-up. Refer to **Section 13** for how missing data will be handled.

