13.1 General Aspects of Analysis

Novapak Nasal Sinus Packing and Stent Study is a prospective, non-randomized, non-blinded, multi-site, investigational, clinical study.

Medtronic Business Restricted

The statistical analyses will be performed by Medtronic employed statisticians. The study population is defined as all eligible patients who signed the Patient Informed Consent Form.

All data collected from enrolled subjects will be utilized in the analyses as appropriate. Analyses of the primary and secondary endpoints will be descriptive.

All continuous variables will be summarized as the number of subjects, means, standard deviations, medians, minimums, maximums, and interquartile ranges. Categorical variables will be summarized as frequencies and percentages.

Any deviations from the original statistical plan will be summarized in the Clinical Study Report(s) (CSRs), along with the justification for the deviations.

No statistical techniques will be used to impute missing data for continuous or categorical outcomes. If a subject's data are missing for any reason, that subject will not be included in that portion of the analysis. The number of subjects included in each analysis will be reported so that the reader can assess the potential impact of missing data.

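### For treated subjects who discontinue for safety or lack of effectiveness, adverse events that arise or become reportable between exit and Day 30 cannot reach the primary safety endpoint

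*Protocol*

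**What the plan says.** The primary safety endpoint covers AEs attributed to the device or of undetermined cause, collected from treatment to study completion. Protocol 4.1.1.1.1 says of it: "This endpoint will be analyzed by calculating the point estimate with a confidence interval of its rate".

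For a subject who completes, that section requires the Day 30 visit, the conclusion of outstanding AE follow-up and a Study Exit form. For one who leaves early, "study completion will be the date of withdrawal or the date the subject meets the definition of lost to follow-up". Section 11.1 likewise ends AE collection at exit if that comes before the Day 30 visit, and 11.3 lets follow-up of an open AE stop at exit.

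Section 9.17.1 contains four statements that bear on this:

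- Before exit, "it is recommended to follow the subject until all ongoing system and/or procedure related AEs are resolved or unresolved with no further actions planned".
- "All data available through the time of the subject's exit will be used for analysis".
- "Upon exiting from the study, no further study data will be collected or study visits will occur for the subject".
- After discontinuation for safety or lack of effectiveness, "the subject shall be asked to be followed for collecting safety data outside the clinical investigation".

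Section 9.17.5 limits investigator withdrawals and adds: "Early removal of Novapak (within the first 7 days of application) alone may not be a reason for subject withdrawal". For missing safety data, 4.1.1.1.1 refers to Section 13. There, as in SAP 7.4, nothing is imputed, and if a subject's data are missing "that subject will not be included in that portion of the analysis".

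**The concern.** Safety is the primary objective. The subjects sent to follow-up outside the study are those in whom something has gone wrong or the device has not worked as hoped. The plan asks for their safety data but gives those data no route to the AE eCRF or the endpoint. Follow-up is therefore cut short for reasons linked to the outcome being measured.

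The device is applied once, so its removal does not require an end to data collection. The study supports a CE Mark submission (Protocol 3.2), and Appendix A reports no previous clinical studies of the device. There is thus little other clinical evidence against which a gap in this rate could be judged.

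**Working it through.** **1. Where each event falls.** No figure in the plan depends on this rule, so the check is to read 4.1.1.1.1, 9.7, 9.17.1, 11.1 and 11.3 together and place each kind of event against the date of exit.

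- *AE recorded before exit, including the one that prompts it.* Inside the window. Section 9.7 has AEs reported as they happen, and 9.17.1 uses all data through exit. Kept.
- *New AE after exit and before Day 30.* Outside the window. Not captured.
- *Complaint present at exit but not yet reportable.* Table 8 in 11.1 waives reporting of expected post-surgical events for a set period unless they worsen or outlast it: mild bleeding 5 days, inflammation and swelling 7, moderate pain 7, nasal congestion 10. A subject who leaves on day 5 because of moderate pain or swelling may have nothing reportable. If it persists past day 7 it becomes reportable, but by then the subject is out. Section 10.1 lists post-operative bleeding (3 reports) and edema and pain (2 reports) among field complaints, so this case is realistic.
- *AE open at exit.* Pre-exit follow-up is only recommended. Later worsening or a change in seriousness or relatedness is not recorded.
- *Adhesions.* Listed as a packing risk in 10.1, with scheduled scoring only at Days 14 and 30 (9.1). A subject who exits earlier is not scored.

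**2. Size, by illustration only.** The documents give no expected AE rate, exit rate or confidence level, and they state that the minimum of 75 was not determined by statistical methods, so there is no stated calculation to reproduce. Assumptions: 75 treated subjects, a per-subject rate and two-sided 95% Clopper-Pearson limits.

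With x subjects having a qualifying AE recorded by exit, and m more whose first such AE falls after exit:

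- Observed rate = x/75; rate with full capture = (x + m)/75; shortfall = m/75.
- m = 1: 1/75 = 1.3 points. m = 3: 3/75 = 4.0 points.
- Limits for y events among n = 75: lower = 2.5% quantile of Beta(y, n − y + 1); upper = 97.5% quantile of Beta(y + 1, n − y).

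| x recorded | Observed (95% CI) | m = 1 captured | m = 3 captured |
|---|---|---|---|
| 2 | 2.7% (0.3–9.3) | 3/75 = 4.0% (0.8–11.2) | 5/75 = 6.7% (2.2–14.9) |
| 4 | 5.3% (1.5–13.1) | 5/75 = 6.7% (2.2–14.9) | 7/75 = 9.3% (3.8–18.3) |
| 6 | 8.0% (3.0–16.6) | 7/75 = 9.3% (3.8–18.3) | 9/75 = 12.0% (5.6–21.6) |

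**3. Cross-check.** If 4 subjects have a recorded device AE and that AE makes some of them leave, the per-subject rate stays at 4/75 = 5.3% whether 0 or 3 of the 4 exit. Only a first qualifying AE after exit changes it.

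**The case against.** Three stronger readings are tempting, and the documents do not support them.

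*The AE that drives a subject out is lost.* It is not. It precedes the exit, lies within the windows of 4.1.1.1.1 and 11.1, and is used under 9.17.1.

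*Section 13 removes the early leaver and the AE with them.* On that reading, 4 recorded events with 3 exits would become 1/72 = 1.4% (0.0–7.5) instead of 4/75 = 5.3%. But a recorded AE is not missing data. SAP 7.4 opens by basing the analysis on all observed data, and 9.17.1 agrees. The rules lack a safety exemption and SAP 7.9.1 gives no denominator, so a clarification is worth having, but the text does not direct this loss.

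*Every early exit lowers the rate.* It does not. A subject already counted stays counted. Dropping an event-free subject raises the rate slightly: 2/74 = 2.70% against 2/75 = 2.67%.

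The best defence is that the affected group should be small. Subjects are urged to stay, investigator withdrawal needs compelling medical justification, and early removal alone may not justify it. Some exits will be withdrawals of consent, where collection must stop anyway. The analysis is descriptive with no threshold, and the intervals in the illustration overlap heavily. All of this stands, and it limits the likely size. It does not close the gap: 9.17.1 foresees AE-related exits, and safety data gathered afterwards have no place in the endpoint.

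**Conclusion.** The point holds as a narrow gap. For treated subjects who discontinue for safety or lack of effectiveness, AEs that first arise or become reportable after exit and before Day 30, and updates to AEs open at exit, do not enter the primary safety endpoint. The truncation is related to outcome. Unrecorded events can only lower the count. A lost relatedness update could move an event into or out of the endpoint, but either way it goes unrecorded.

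The size cannot be derived from the documents. The 1.3 points per subject assumes 75 treated subjects and a first qualifying AE after exit. The range of 1.3 to 4.0 points further assumes one to three such subjects. Neither is an estimate of what will happen. This is an inexpensive improvement to a primary safety rate, and it does not invalidate the study.

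**What to change.** 1. In Protocol 9.17.1, and consistently in 4.1.1.1.1, 11.1 and 11.3, state that a treated subject who discontinues for safety or lack of effectiveness stays on AE and device deficiency collection inside the study, by visit or phone, through the Day 30 window (to Day 42, from the +12 in 9.1), unless consent to data collection is revoked. AEs go on the AE eCRF and count in the primary and all-AE summaries.
2. Limit the rule that study data stop at exit to subjects who revoke consent or cannot be reached.
3. As a clarification in Protocol 13.1 and SAP 7.4, state that AEs recorded before exit always count and that treated subjects are not removed from the safety rate because of early exit. Report the number followed to Day 30 beside the rate.

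The cost is a protocol and SAP wording amendment, a few extra contacts, and possibly a slightly less favourable AE rate.
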